Appendix 3 Management of Cobimetinib plus Atezolizumab–Associated Adverse Events (Arm A) (cont.)

Table 7 Recommended Dose Modifications for Cobimetinib in Patients with Left Ventricular Ejection Fraction Decrease from Baseline

Patient	LVEF value	Recommended action with cobimetinib and atezolizumab	LVEF value following treatment break	Recommended cobimetinib daily dose
Asymptomatic	≥ 50% (or 40%–49% and < 10% absolute decrease from BL)	Continue at current dose	N/A	N/A
	< 40% (or 40%–49% and ≥ 10% absolute decrease from BL)	Interrupt treatment for 2 weeks Continue atezolizumab as clinically indicated	< 10% absolute decrease from BL	First occurrence: 40 mg
				Second occurrence: 20 mg
				Third occurrence: permanent discontinuation
< 40% (or ≥ 10% absolute decrease from BL)	Permanent discontinuation			
Symptomatic	N/A	Interrupt treatment for 4 weeks. Consider withholding atezolizumab Discuss with Medical Monitor regarding resumption of atezolizumab. Cardiology consultation is strongly recommended.	Asymptomatic and < 10% absolute decrease from BL	First occurrence: 40 mg
				Second occurrence: 20 mg
				Third occurrence: permanent discontinuation
			Asymptomatic and < 40% (or ≥ 10% absolute decrease from BL)	Permanent discontinuation
Symptomatic regardless of LVEF	Permanent discontinuation			

BL = baseline; LVEF = left ventricular ejection fraction; N/A = not applicable.

**Appendix 3 Management of Cobimetinib plus Atezolizumab–Associated
Adverse Events (Arm A) (cont.)**
**GUIDELINES FOR MANAGEMENT OF PATIENTS WHO EXPERIENCE
ELEVATED CPK AND RHABDOMYOLYSIS**

Elevated CPK has been reported with cobimetinib (see Section [5.1.1.2](#)). See [Table 8](#) for guidelines for management of elevated CPK and rhabdomyolysis.

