 - Patients with active malignancy (other than CRC) or a prior malignancy within the past 3 years are excluded. Patients with completely resected cutaneous melanoma (early stage), basal cell carcinoma, cutaneous squamous cell carcinoma, cervical carcinoma in-situ, breast carcinoma in-situ, and localized prostate cancer are eligible.

Exclusion criteria based on organ function or medical history:

Cardiovascular:

- Unstable angina, new onset angina within last 3 months, myocardial infarction within last 6 months and current congestive heart failure New York Heart Association Class II or higher.
- Left ventricular ejection fraction (LVEF) below institutional lower limit of normal or below 50%, whichever is lower.
- Poorly controlled hypertension, defined as a blood pressure consistently above 150/90 mmHg despite optimal medical management.

Infections:

- HIV infection
- Active tuberculosis infection
- Severe infections within 2 weeks prior to Cycle 1 Day 1
- Signs or symptoms of significant infection within 2 weeks prior to Cycle 1 Day 1
- Received oral or IV antibiotics within 2 weeks prior to Cycle 1 Day 1

Patients receiving prophylactic antibiotics (e.g., for prevention of urinary tract infection or chronic obstructive pulmonary disease) are eligible

- Active or chronic viral hepatitis B or C infection
 1. Patients with hepatitis B virus (HBV) infection are eligible if test for hepatitis B surface antigen (HBsAg) and HBV DNA are negative
 2. Patients with hepatitis C virus (HCV) infection are eligible if polymerase chain reaction (PCR) test for HCV RNA is negative.

Ocular:

- History of or evidence of retinal pathology on ophthalmologic examination that is considered a risk factor for central serous retinopathy, retinal vein occlusion, or neovascular macular degeneration
- Patients will be excluded if they currently have any of the following risk factors for retinal vein occlusion:
 1. Uncontrolled glaucoma with intra ocular pressure ≥ 21 mmHg
 2. Uncontrolled hypercholesterolemia > 300 mg/dL or 7.75 mmol/L
 3. Uncontrolled hypertriglyceridemia > 300 mg/dL or 3.42 mmol/L
 4. Fasting hyperglycemia > 160 mg/dL or 8.9 mmol/L

Autoimmune conditions and immunomodulatory drugs:

- History of autoimmune disease except for the following:
 1. Patients with autoimmune hypothyroidism on a stable dose of thyroid replacement hormone are eligible.
 2. Patients with controlled type 1 diabetes mellitus on a stable dose of insulin regimen are eligible.

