4.5.8 Left Ventricular Ejection Fraction

All patients will require evaluation of LVEF at screening, and only patients receiving cobimetinib (Arm A) will require subsequent evaluations of LVEF.

Evaluation of LVEF by ECHO or MUGA must be performed at the following timepoints:

- Screening
- Cycle 2 Day 1 \pm 1 week
- Day 1 of every three treatment cycles thereafter starting at Cycle 5 \pm 2 weeks
- Treatment discontinuation visit: The treatment discontinuation visit evaluation of LVEF does not need to be performed at the treatment discontinuation visit if an evaluation has been performed within the last 12 weeks and there are no clinically significant findings and/or changes from baseline.
- All patients who restart treatment with a reduced dose of cobimetinib because of a decrease in LVEF should have LVEF measurements taken after approximately 2 weeks, 4 weeks, 10 weeks, and 16 weeks and then resume monitoring LVEF every 3 cycles.

Any patient who develops clinical signs or symptoms suspicious of cardiac failure should undergo an LVEF assessment. Evaluation of LVEF must be performed by the same method (ECHO or MUGA) for each patient. It is strongly encouraged that the same laboratory and operator perform ECHO/MUGA scans for each individual patient. Investigators must be aware of local institution regulations regarding repeat MUGA scans. The repeat administration of radioisotopes is limited in some nuclear medicine laboratories, and some patients in this study could require monitoring on four or more occasions.

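### The LVEF restart row in Appendix 3, Table 7 has no 40% floor, so with a baseline below 50% one after-break value can call for both restarting cobimetinib and stopping it for good

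*Protocol*

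**What the plan says.** Table 7 has an asymptomatic and a symptomatic block.

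- **Asymptomatic, entry to a break:** cobimetinib is interrupted for 2 weeks when LVEF is "< 40% (or 40%–49% and ≥ 10% absolute decrease from BL").
- **Asymptomatic, after the break, restart:** the condition is "< 10% absolute decrease from BL". The dose is 40 mg at the first occurrence and 20 mg at the second; at the third, cobimetinib stops.
- **Asymptomatic, after the break, stop:** permanent discontinuation at "< 40% (or ≥ 10% absolute decrease from BL").
- **Symptomatic, after a 4-week break:** the same pair is repeated for patients whose symptoms have cleared. Restart requires "Asymptomatic and < 10% absolute decrease from BL"; permanent discontinuation applies at "Asymptomatic and < 40% (or ≥ 10% absolute decrease from BL"). A patient who is still symptomatic stops whatever the LVEF.

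The Cardiovascular criteria in Section 4.1.2 exclude a baseline LVEF "below institutional lower limit of normal or below 50%, whichever is lower". Section 4.5.8 says that patients restarting at a reduced dose because of an LVEF decrease "should have LVEF measurements taken after approximately 2 weeks, 4 weeks, 10 weeks, and 16 weeks".

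The paragraph introducing Table 7 addresses only cardiac symptoms that do not improve after interruption. The table's footnote lists abbreviations. Neither says which row prevails when two apply.

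**The concern.** The restart and stop rows should divide the possible after-break results between them. The stop row applies if either of two things is true: LVEF is under 40%, or it has fallen at least 10 points. The restart row negates only the second. A low absolute value close to a low baseline therefore satisfies both rows, and at a first or second occurrence they give opposite instructions.

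Left ventricular dysfunction is an important identified risk of cobimetinib (Section 5.1.1.1, which reports Grade 2 or 3 decreases in 8.5% versus 3.7% of patients in the Phase III study with vemurafenib), and that section sends sites to Appendix 3 for management. Taken literally, the restart row re-doses a patient whose LVEF is still at a level where the table's own entry row says to interrupt. Two sites could treat identical patients differently and both be following the table.

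**Working it through.** No stated figure needs reproducing; the check is logic plus enumeration.

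**Inputs.** Let *b* be baseline LVEF and *v* the value after the break, reading the 10% absolute decrease as 10 percentage points.

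- Restart (Table 7): *b* − *v* < 10
- Stop (Table 7): *v* < 40, or *b* − *v* ≥ 10
- Eligible (Section 4.1.2): *b* ≥ the smaller of the site's lower limit and 50

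**When both rows apply.** Restart rules out *b* − *v* ≥ 10, so the stop row can be met at the same time only through *v* < 40. Together:

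*b* − 10 < *v* < 40, which requires *b* < 50.

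For *b* ≥ 50, any *v* below 40 is a fall of more than 10 points and only the stop row applies.

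**Example.** With *b* = 47 and *v* = 38, the fall is 47 − 38 = 9 < 10, so restart applies; 38 < 40, so stop applies.

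**No recovery is needed.** For *b* < 50, the second entry condition (40%–49% with a fall of at least 10 points) cannot be met, because *b* − 10 < 40. Such a patient enters the break only through LVEF under 40%. With *b* = 47 and an on-treatment value of 38, the patient is interrupted. If the value is still 38 after the break, the restart row is met with no change in LVEF.

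**Enumeration in whole points, baselines 40 to 70.**

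| Baseline | After-break values meeting both rows | Count |
|---|---|---|
| 49 or higher | none | 0 |
| 48 | 39 | 1 |
| 47 | 38–39 | 2 |
| 46 | 37–39 | 3 |
| 45 | 36–39 | 4 |
| 44, 43, 42, 41 | up to 39 | 5, 6, 7, 8 |
| 40 | 31–39 | 9 |

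The total is 1 + 2 + … + 9 = 45 pairs. If LVEF is recorded in tenths, a baseline of 49 also overlaps, at 39.1 to 39.9.

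**Dependence on the site limit.** The documents give no institutional limits, so these are assumptions:

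- 45%: 4 + 3 + 2 + 1 = 10 pairs
- 47%: 2 + 1 = 3 pairs
- 48%: 1 pair
- 49%, or 50% and above: none

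These counts show where the overlap lies. They are not frequencies.

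**After the fix.** With restart redefined as *b* − *v* < 10 and *v* ≥ 40, the enumeration finds no pair meeting both rows and none meeting neither, in whole points and in tenths.

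**The case against.** The logic is hard to dispute; the objections are about weight.

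- **Reachability is conditional.** If every site uses a lower limit of 50% or more, no eligible patient can fall in the overlap. Most of the 45 pairs come from baselines of 40% to 44%, and nothing in the documents indicates site limits that low. This stands, and is why no patient number is given.
- **The table leans towards stopping.** LVEF under 40% is by itself enough for the stop row and enough for the asymptomatic interruption row, so a patient restarted at 38% would at once qualify for another interruption. A careful clinician would probably stop. That is a fair inference about intent, but it is not a written precedence rule, and the table exists to guide exactly this decision.
- **Other safeguards limit the harm.** Section 4.6.2 requires stopping for a medical condition that may jeopardize safety. Section 5.2.3 makes symptomatic heart failure or Grade ≥ 3 LVEF reduction immediately reportable. Section 4.5.8 schedules repeat LVEF after a reduced-dose restart and an assessment for suspicious cardiac symptoms. The symptomatic block strongly recommends a cardiology consultation, and the table's title calls its modifications recommended. All of this reduces the consequence; none of it settles which row applies. The first scheduled repeat LVEF comes about 2 weeks after dosing has resumed.

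**Conclusion.** The concern holds: the table is wrong as written. Both rows are met whenever the after-break LVEF is under 40% and less than 10 points below baseline, in both blocks of Table 7.

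The scope is narrow. It affects Arm A only, and only first and second occurrences, since both rows stop cobimetinib at the third. It needs a baseline under 50% (48% or lower in whole points), hence a site whose lower limit is under 50%. How many patients this involves cannot be estimated without the sites' limits and the baseline LVEF distribution, which the documents do not give; the case is likely rare. It does not touch the OS endpoint, the tests, sample size, power or type I error. It is a low-priority correction, worth making because it concerns a safety instruction for an identified risk.

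**What to change.** In Table 7, add **and LVEF ≥ 40%** to the after-break restart row in both the asymptomatic and symptomatic blocks. Alternatively, add one sentence stating that the permanent-discontinuation row takes precedence when both apply. The first option is cleaner because it makes the two rows mutually exclusive and exhaustive.

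The cost is a few words at the next amendment. No assessment, visit or data item changes.

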Appendix 3 Management of Cobimetinib plus Atezolizumab–Associated Adverse Events (Arm A) (cont.)

Table 8 Recommended Dose Modifications for Cobimetinib and Atezolizumab in Patients with CPK Elevations and Rhabdomyolysis

Description	Management
General guidance	Rule out cardiac cause (check ECG, serum cardiac troponin, and CPK-isoforms M and B fraction) and rule out rhabdomyolysis (clinical examination; serum creatinine, potassium, calcium, phosphorus, uric acid, and albumin; and urine myoglobin). Assess patient for any history of strenuous physical activity, blunt trauma, or recent IM injections.
Asymptomatic CPK elevations Grade 1–3	Cobimetinib dosing and atezolizumab do not need to be modified or interrupted to manage asymptomatic Grade ≤ 3 CPK elevations
Asymptomatic CPK elevations Grade 4	Interrupt cobimetinib and atezolizumab treatment. If improved to Grade ≤ 3 within 4 weeks, restart cobimetinib at a dose reduced by 20 mg, if clinically indicated. If CPK elevations do not improve to Grade ≤ 3 within 4 weeks following dose interruption, permanently discontinue cobimetinib treatment. Resumption of atezolizumab may be considered in patients who are deriving benefit. ^{a,b,c}
Rhabdomyolysis or symptomatic CPK elevations	Interrupt cobimetinib and atezolizumab treatment. If improved to Grade ≤ 3 within 4 weeks, restart cobimetinib at a dose reduced by 20 mg, if clinically indicated. If CPK elevations do not improve to Grade ≤ 3 within 4 weeks following dose interruption, permanently discontinue cobimetinib treatment Resumption of atezolizumab may be considered in patients who are deriving benefit. ^{a,b,c}

^a If corticosteroids have been initiated, they must be tapered over ≥ 1 month to ≤ 10 mg/day oral prednisone or equivalent before atezolizumab can be resumed.

^b Atezolizumab may be withheld for a period of time beyond 12 weeks to allow for corticosteroids to be reduced to ≤ 10 mg/day oral prednisone or equivalent. The acceptable length of the extended period of time must be agreed upon by the investigator and the Medical Monitor.

^c Resumption of atezolizumab may be considered in patients who are deriving benefit and have fully recovered from the immune-related event. Patients can be rechallenged with atezolizumab only after approval has been documented by both the investigator (or an appropriate delegate) and the Medical Monitor.

**Appendix 3 Management of Cobimetinib plus Atezolizumab–Associated
Adverse Events (Arm A) (cont.)**

**GUIDELINES FOR MANAGEMENT OF PATIENTS WHO EXPERIENCE
HEMORRHAGE**

Hemorrhage has been reported with cobimetinib (see Section 5.1.1.2). See Table 9.

Table 9 Recommended Dose Modifications for Cobimetinib in Patients with Hemorrhage

Hemorrhage	
Grade 3 events	Interrupt cobimetinib treatment. There are no data on the effectiveness of cobimetinib dose modification for hemorrhage events. Clinical judgment should be applied when considering restarting Cobimetinib treatment. Continue atezolizumab treatment.
Grade 4 hemorrhage or any grade cerebral hemorrhage	Interrupt cobimetinib treatment. Permanently discontinue cobimetinib for hemorrhage events attributed to cobimetinib. Continue atezolizumab treatment.

SYSTEMIC IMMUNE ACTIVATION

Systemic immune activation is a rare condition characterized by an excessive immune response. Given the mechanism of action of atezolizumab, systemic immune activation is considered a potential risk when given in combination with other immunomodulating agents.

Recommendations regarding early identification and management of systemic immune activation are provided below. In the event of suspected systemic immune activation, atezolizumab should be withheld and the Medical Monitor should be contacted immediately for additional guidance.

Early disease recognition is critical, and systemic immune activation should be suspected if, in the absence of an alternative etiology, the patient meets two or more of the following criteria:

- Hypotension that is refractory to aggressive IV fluid challenge
Vasopressor support may be required.
- Respiratory distress that requires aggressive supportive care
Supplemental oxygen and intubation may be required.
- Fever > 38.5°C
- Acute renal or hepatic failure
- Bleeding from coagulopathy

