retinal pathology that is considered to be a risk factor for or indicative of neurosensory retinal detachment, central serous chorioretinopathy, neovascular retinopathy, or retinopathy of prematurity. Patients will also undergo ophthalmologic examinations at specified time points throughout the study (see [Appendix 1](#)). Details regarding baseline and subsequent ophthalmologic examinations are provided in [Appendix 3](#).

Guidelines for management of patients who develop Grade ≥ 2 visual disorders or retinopathy are provided in [Appendix 3](#).

Left Ventricular Dysfunction

Decrease in left ventricular ejection fraction from baseline has been reported in patients receiving cobimetinib. Left ventricular dysfunction may occur with signs and symptoms of cardiac failure, or reduction in left ventricular ejection fraction events may be asymptomatic.

Left ventricular dysfunction has been characterized in the Phase III Study GO28141. The study incorporated prospective serial left ventricular ejection fraction evaluation in all patients. With active surveillance, measured reductions in left ventricular ejection fraction were observed more frequently in patients treated with cobimetinib plus vemurafenib than placebo plus vemurafenib (8.5% vs. 3.7%, respectively, of Grade 2 or 3 decrease). Of the patients treated with cobimetinib plus vemurafenib, 2 patients (0.8%) had symptomatic reduction in left ventricular ejection fraction and the remaining patients were asymptomatic. Most left ventricular ejection fraction reduction events in patients on cobimetinib plus vemurafenib (62%) improved or resolved with management according to the dose-modification guidelines (see [Appendix 3](#)).

Rhabdomyolysis and CPK Elevations

Elevations in CPK have been observed in patients who received cobimetinib monotherapy as well as when administered with other agents. The majority of CPK elevations reported were asymptomatic, non-serious, and resolved with or without study drug interruption. One event of rhabdomyolysis was reported in the Phase III Study GO28141 (cobimetinib plus vemurafenib), and rhabdomyolysis has been reported in postmarketing experience.

In Study GO28141, elevated CPK was reported as an adverse event more frequently in patients treated with cobimetinib plus vemurafenib (32.4% all grades, 11.3% Grade ≥ 3 events) than placebo plus vemurafenib (8.1% all grades, 0% Grade ≥ 3 events).

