5.1.4.1 **Cobimetinib and Regorafenib Dose Modifications**

Cobimetinib and regorafenib dose modifications are provided in [Table 3](#).

Table 3 Recommended Cobimetinib and Regorafenib Dose Modifications

Grade (CTCAE) ^a	Recommended Cobimetinib Dose	Recommended Regorafenib Dose
Grade 1 or Grade 2 (tolerable)	No dose reduction. Maintain cobimetinib at the same dose of 60 mg QD (3 tablets)	No dose reduction. Maintain regorafenib at the same dose of 160 mg QD (4 tablets)
Grade 2 (intolerable) or Grade 3 or 4 (any)		
First appearance	Interrupt treatment until Grade ≤ 1 , restart treatment at 40 mg QD (2 tablets)	Interrupt treatment until Grade ≤ 1 , restart treatment at 120 mg QD (3 tablets)
Second appearance	Interrupt treatment until Grade ≤ 1 , restart treatment at 20 mg QD (1 tablet)	Interrupt treatment until Grade ≤ 1 , restart treatment at 80 mg QD (2 tablets)

Grade (CTCAE) ^a	Recommended Cobimetinib Dose	Recommended Regorafenib Dose
Third appearance	Consider permanent discontinuation	Consider permanent discontinuation

CTCAE = Common Terminology Criteria for Adverse Events; NCI = National Cancer Institute; QD = once daily.

^a The intensity of clinical adverse events graded by NCI CTCAE v4.0.

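### Protocol Appendix 3, Table 8: for rhabdomyolysis or symptomatic CPK elevation entered at CPK Grade 1–3, the Grade ≤ 3 restart and stop thresholds give no guidance on ending the cobimetinib hold

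*Protocol*

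**What the plan says.** Protocol Appendix 3, Table 8 sets cobimetinib and atezolizumab handling for CPK events in Arm A. Below a general-guidance row it has three rows.

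- **Asymptomatic, Grade 1–3.** No change is required: "Cobimetinib dosing and atezolizumab do not need to be modified or interrupted to manage asymptomatic" elevations up to Grade 3.
- **"Asymptomatic CPK elevations Grade 4".** Both drugs are interrupted, followed by the restart and stop sentences below.
- **"Rhabdomyolysis or symptomatic CPK elevations".** The instruction is "Interrupt cobimetinib and atezolizumab treatment". The restart sentence is "If improved to Grade ≤ 3 within 4 weeks, restart cobimetinib at a dose reduced by 20 mg, if clinically indicated". The stop sentence is "If CPK elevations do not improve to Grade ≤ 3 within 4 weeks following dose interruption, permanently discontinue cobimetinib treatment".

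The last two rows carry the same text. The third names no CPK grade for entry, no minimum length of hold, and no condition on the symptoms or the rhabdomyolysis. Resuming atezolizumab is a separate, discretionary step under footnotes a to c.

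Section 5.1.4.1, Table 3 gives the general cobimetinib schedule. For an intolerable Grade 2 event or any Grade 3 or 4 event it says "Interrupt treatment until Grade" ≤ 1, with restart at a lower dose. Sections 5.1.1.1 and 5.1.4.3 send sites to Appendix 3 for CPK elevation and rhabdomyolysis.

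**The concern.** The test for leaving the symptomatic row does not match the reason for entering it. Entry depends on symptoms or rhabdomyolysis; exit depends on a grade threshold that fits a Grade 4 starting point. A site with a symptomatic patient below Grade 4 finds a restart condition that is already satisfied and a stop condition that is out of reach, so the table does not say what should end the hold.

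Section 5.1.1.1 lists rhabdomyolysis and CPK elevation among the important identified risks of cobimetinib. Section 5.2.3 makes rhabdomyolysis an adverse event of special interest whatever the CPK grade. The row is thus a patient-level safety instruction that sites would apply as written. What is at stake is consistent handling of these patients, both between sites and between Table 8 and Table 3. No endpoint, error rate, power figure or efficacy analysis depends on it.

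**Working it through.** The plan gives no figure to reproduce. The check compares each possible CPK grade at entry with the two thresholds, reading Grade in the restart sentence as CPK grade. The stop sentence, which names CPK, supports that reading.

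| CPK grade at entry to the symptomatic row | Restart threshold (Grade ≤ 3) at interruption | Stop threshold (not Grade ≤ 3 by 4 weeks) |
|---|---|---|
| 1 | already met | not met unless CPK becomes Grade 4 and stays there |
| 2 | already met | same |
| 3 | already met | same |
| 4 | not met; a real improvement is needed | met if Grade 4 persists |

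The thresholds discriminate at 1 of 4 entry grades and not at the other 3. In the asymptomatic Grade 4 row every patient starts at Grade 4, so the same sentences work there.

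Entry below Grade 4 is a real possibility under the table. Asymptomatic Grade 1–3 elevation needs no interruption, so at those grades symptoms or rhabdomyolysis are exactly what moves a patient into the symptomatic row.

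**Comparison with Table 7 in the same appendix.** For reduced ejection fraction, symptomatic patients are handled separately. Restart there requires the patient to be asymptomatic, and persisting symptoms lead to discontinuation whatever the ejection fraction. This shows only that the protocol links exit to the entry trigger elsewhere; it does not settle what Table 8 should say.

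**Comparison with Table 3.** For a symptomatic Grade 3 CPK elevation, Table 3 holds cobimetinib until Grade ≤ 1, while the Table 8 threshold of Grade ≤ 3 is met at once. Section 5.1.4.2 describes the event-specific guidance as additional and does not say which table prevails.

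**Size.** Section 5.1.1.1 reports CPK elevation as an adverse event in 32.4% of patients (all grades) and 11.3% (Grade ≥ 3) with cobimetinib plus vemurafenib.

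- Share of those patients below Grade 3: (32.4 − 11.3) / 32.4 = 21.1 / 32.4 = 65%.
- At the same rates in Arm A (about 180 patients): 0.324 × 180 ≈ 58 with any CPK event, and 0.113 × 180 ≈ 20 at Grade ≥ 3.

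These figures are context only. They come from a different combination, and the documents give neither the symptomatic share nor the Grade 4 share. An assumed symptomatic share of 5% to 20% would put 3 to 12 of the 58 in this row, but that range is illustrative and has no source in the documents.

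**The case against.** The strongest reply is that the row is not as empty as the threshold makes it look. It orders interruption of both drugs. Cobimetinib may return only at a reduced dose and subject to clinical indication. Atezolizumab is resumed under its own conditions, including documented approval. Section 4.6.2 requires treatment to stop for intolerable toxicity or a condition that jeopardises safety. Rhabdomyolysis must be reported to the sponsor within 24 hours. All of this stands, and it rules out three stronger readings that a reader might infer.

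- **That the row never holds the drug.** It does; what is missing is a working criterion for ending the hold.
- **That a patient with active rhabdomyolysis is to be restarted straight away.** The clinical-indication proviso prevents that.
- **That the discontinuation line can never be reached.** It can be, when CPK is Grade 4 at entry or becomes Grade 4 and stays there.

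A second reply is that Grade in the restart sentence may mean the grade of the event rather than of CPK. That is possible, but an event graded 1 to 3 would also meet the test at once. Reading improvement as an actual fall in grade does not help either. A symptomatic patient whose CPK stays at Grade 2 for 4 weeks has not improved, and the stop sentence could then be taken to require permanent discontinuation. The same words would support opposite actions.

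A third reply concerns Table 3. Table 8 visibly departs from the general schedule on purpose, since asymptomatic Grade 3 needs no interruption. Table 4 also lets treatment continue, at the investigator's discretion, through Grade ≥ 3 toxicity that is primarily a laboratory abnormality. Together with the routing to Appendix 3, this softens the mismatch. It does not remove it, because no precedence is stated and the symptomatic row is not a purely laboratory finding.

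The objection that the affected group may be small, with "One event of rhabdomyolysis was reported in the Phase III Study GO28141 (cobimetinib plus vemurafenib"), is fair on frequency but leaves the logic of the row unchanged.

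**Conclusion.** The point holds in this form: for patients who enter the symptomatic row at CPK Grade 1–3, the restart threshold is already met at interruption and the stop threshold cannot be met unless CPK becomes Grade 4. Beyond clinical indication, the row gives no criterion for ending the cobimetinib hold, and it does not mention the symptoms or rhabdomyolysis that triggered it. It is also unreconciled with Table 3.

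The size is three of the four possible entry grades; a patient count cannot be derived. The conclusion rests on the wording of Table 8 and on reading Grade as CPK grade; the alternative readings do not repair it. Because a stated safety rule fails for most of its entry grades, this is an error to correct rather than a detail left open. The documents do not support the claim that the row leaves cobimetinib running or makes permanent discontinuation impossible.

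**What to change.** The sponsor should reconcile the restart and discontinuation conditions of the symptomatic row with that row's own entry condition and with the other Table 8 rows. It should make clear whether Grade means CPK grade or event grade, and state whether Table 8 or Table 3 governs cobimetinib for CPK elevation and rhabdomyolysis. Which clinical criterion applies is for the sponsor to decide; none is proposed here. The cost is one table row and one sentence on precedence in a protocol amendment, with no effect on sample size, analysis timing or the SAP.
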